The primary outcome of the study is to determine differences in glycemic control as measured by mean daily blood glucose concentration between treatment groups. For each subject, we will take the average of all pre-meal and bedtime glucose values collected after the first day of therapy during the hospital stay (up to 10 days).

Secondary outcomes include differences between treatment groups in any of the following measures:

1. Differences in mean daily glucose in patients admitted to medicine and surgery services.
2. Differences in mean daily glucose in patients with admission HbA1c lower than and higher than 8%.
3. Differences in mean daily glucose in patients with length of stay shorter and longer than 3 and 5 days.
4. Proportion of BG readings within target of 80 mg/dl and 180 mg/dl before meals.
5. Number of BG readings between 80 mg/dl and 180 mg/dl before meals without hypoglycemia.
6. Number of patients with hypoglycemia (defined as a BG < 70 mg/dl) and number of events adjusted by length of stay (event rate).
7. Number of patients with severe hypoglycemia (defined as a BG < 40 mg/dl) and number of events adjusted by length of stay (event rate).
8. Length of hospital stay.
9. Cardiac complications are defined as myocardial infarction, cardiac arrhythmia requiring medical treatment, or cardiac arrest.
10. Acute renal failure defined as a clinical diagnosis with documented new-onset abnormal renal function (increment in serum creatinine > 0.5 mg/dL from baseline).
11. Hospital mortality.

IV.d. Plan. This study will include male or female subjects > 18 years. Due to the design of this study, there will be no run-in period. Upon arrival to the emergency department or medical or general surgical wards, subjects will be screened. Patients with a known history of T2D treated with diet alone, any combination of OADs, and insulin prior to admission will be considered potential candidates for this study. Patients treated with degludec, glargine U300 or with long-acting GLP1-RA (dulaglutide, albiglutide and weekly exenatide) prior to admission will be excluded. Patients admitted with acute or chronic medical illnesses, emergency or elective surgical procedures and trauma would be included in the study. The goal of insulin therapy is to maintain fasting and pre-meal blood glucose levels between 80 mg/dl and 180 mg/dL while avoiding hypoglycemia.

A total of 180 patients with T2D with a blood glucose > 140 mg/dL and < 400 mg/dL will be randomized to receive:

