- If a patient develops hypoglycemia (BG <70 mg/dL), the insulin TDD (basal and prandial) should be decreased by 20%.
- If a patient develops severe hypoglycemia (BG <40 mg/dL), the insulin TDD (basal and prandial) should be decreased by 30-40%.

IV.g. Data Analysis:

Aim 1. To determine differences in inpatient glycemic control, as measured by mean daily blood glucose concentration and frequency of hypoglycemia, in general medicine and surgery patients with T2D treated with basal bolus regimen with glargine U300 and U100 plus glulisine insulin before meals.

Due to the lack of efficacy and safety data with the use of glargine U300 in the inpatient setting, periodic conduct interim analyses will be conducted every 6 months to monitor the primary outcome and rate of hypoglycemia, and to modify the study design regarding interval of administration and dosage adjustment for basal insulin (see page 9, Data Safety Monitoring Plan, sections IV. f. and IV.g.).

Sample Size and Power Calculations:

The primary endpoint in this study is glycemic control measured by mean daily BG concentration. To show the non-inferiority of glargine U300 and U100 in terms of glycemic control, we set the equivalence margin as 18 mg/dl (1 mosm/l), from a view that a difference <18 mg/dl is usually not considered as clinically significant (12, 14, 16). Based on the results from Rabbit medicine and surgery trials, it is reasonable to assume the standard deviation of mean daily BG is bounded above by 45 mg/dl. Assuming the true BG difference between the treatment groups is zero, and using one-sided, two-sample t-tests, we require 78 subjects for each treatment group to achieve 80% power. Accounting for 10% attrition rate, we would need 90 patients per treatment group, which means 180 subjects in total, to achieve >80% power in Aim 1.

Analysis of Primary Endpoint:

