The primary endpoint for Aim 1 is glycemic control measured by mean daily BG concentration among the two study groups. Blood glucose will be measured before each meal and at bedtime. We will first perform cross-sectional analyses using nonparametric Krustal-Wallis tests (or Wilcoxon tests) or one-way ANOVA, followed by repeated measures ANOVA to estimate and test the difference between the two treatment groups while simultaneously examining mean daily BG across multiple days during treatment. A mixed effect model may be used to further account center effect or other potential confounders for the BG outcome. Stepwise, backward, or forward model selection strategy will be adopted to determine the variables to be included in the final model. Standard diagnostic and model checking procedures will be applied to examine the fit of the developed models.

Analysis of Secondary Endpoints:

Secondary endpoints for Aim 1 in this study include incidence of hypoglycemia, number of hypoglycemic

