events, number of severe hyperglycemia, mean daily fasting BG, daily insulin dose, length of hospital stay, acute renal failure and hospital mortality. Blood glucose will be measured before each meal and at bedtime. For discrete outcomes (such as hypoglycemia outcomes), if the outcome is binary (e.g. with or without hypoglycemia), we will first conduct nonparametric comparisons based on a two-sided Chi-square test (or Fisher's exact test in the presence of low incidence rates), followed by the Cochran-Mantel-Haenszel test, which adjusts for the potential center effect. If the discrete outcome is a count outcome (such as the number of hypoglycemic event), we will perform Poisson regression (or Negative Binomial regression) that adjusts for the length of hospital stay to assess the difference in the count outcome between the treatment groups. We also value the repeated measures analyses based on mixed effect models. This is because they will allow us to assess treatment effect fine tuned according to other confounders of the BG outcomes. By these considerations, we will conduct both types of analyses to provide a thorough evaluation of the hypothesis of interest. For continuous outcomes that are not repeated measures (such as length of hospital stay), we will use two-sample t-tests or nonparametric Wilcoxon tests to compare them between groups. Transformations will be applied if normality violation is detected. Multivariate linear regression will be further conducted to assess the difference in continuous secondary outcomes between the two groups while other relevant covariates. We will use standard model selection and model checking procedures for linear regression to decide the final models and assess their fits to the data.

IV.f. Data and Safety Monitoring Board (DSMB):

The Data and Safety Monitoring Board (DSMB) will review unblended data on safety, treatment compliance, and evaluate the efficacy of the intervention being studied in this clinical trial. The DSMB will meet at 6-month intervals and report on study progress to the IRB.

IV.g. Interim Analysis and Stopping Rules: We plan to perform one interim analysis on the primary endpoint every 6 months and when half of the subjects have been randomized. The trial will be stopped if there is evidence beyond a reasonable doubt of a difference in the rate of death and hospital complications (two-sided alpha level, <0.01) between the treatment groups.

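### Secondary outcome 3 compares arms within length-of-stay groups; stay is a post-randomisation outcome, so these are not randomised comparisons and should be labelled descriptive

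*Combined protocol and SAP*

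**What the plan says.** Section IV.c introduces its list with "Secondary outcomes include differences between treatment groups in any of the following measures", so every item is a comparison of arms. Items 1 and 2 compare mean daily glucose within groups fixed at admission (medicine or surgery service; admission HbA1c below or above 8%). Item 3 is "Differences in mean daily glucose in patients with length of stay shorter and longer than 3 and 5 days". Item 8 of the same list is "Length of hospital stay".

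Section IV.g, Analysis of Secondary Endpoints, treats stay as an endpoint, naming it among "mean daily fasting BG, daily insulin dose, length of hospital stay, acute renal failure and hospital mortality", and plans a between-arm t-test or Wilcoxon test of it.

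The primary outcome in Section IV.c gives each patient one value, the "average of all pre-meal and bedtime glucose values collected after the first day of therapy during the hospital stay (up to 10 days"). For that variable, Section IV.g plans repeated measures ANOVA to compare the arms "while simultaneously examining mean daily BG across multiple days during treatment", and possibly a mixed model. It names no treatment-by-day term and no day window.

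Section IV.e says that the trial is open label and that randomisation is blocked on prior insulin use only. Nothing in the documents labels item 3 descriptive.

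**The concern.** Randomisation makes the arms comparable at entry. It does so within groups defined by admission characteristics, but not within groups defined by something that happens later. If stay is related to glucose and one arm tends to go home sooner, the short-stay patients in the two arms are different kinds of patient, and their glucose can differ with no treatment effect on glucose. The same follows if glucose bears on discharge more strongly in one arm than in the other.

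A second difficulty needs no effect on stay. Each patient's mean runs from day 2 to discharge, so a short-stay mean holds only early days and a long-stay mean is diluted by later ones. Section I says that glargine U300 reaches steady state after the second or third day, so an early lag is a natural question in this trial. Item 3 would show such a lag as a difference between types of patient.

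At stake is the reading of one secondary item out of 11. As listed, it stands beside items 1 and 2 as if it had the same standing.

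**Working it through.** **The plan's own figure.** The claim disputes no number; the sample size is reproduced only to fix the scale. Section IV.g gives SD 45 mg/dl, a true difference of 0, one-sided tests and 80% power, and says "we set the equivalence margin as 18 mg/dl". With one-sided alpha 0.05 (not stated, but it reproduces the result):

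n = 2 × (1.645 + 0.842)² × (45/18)² = 2 × 6.18 × 6.25 = 77.3, so 78 per arm, as stated.

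After 10% attrition from 90, 90 × 0.90 = 81 per arm remain.

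**Inputs for bias.** The documents give no stay distribution, no stay-glucose correlation and no expected effect on stay. Everything in this part is therefore assumed:
- daily glucose with between-patient SD 35 and within-patient SD 25;
- log-normal stay with median 4.5 days and log-SD 0.5, rounded to 1–10 days;
- log stay rising by 0.1 or 0.2 per SD of glucose (the slope).

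The true glucose effect is 0. The table shows the spurious arm difference in mg/dl, with stays of exactly 3 and 5 days put in the shorter group.

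| Change in stay in one arm | Slope | ≤3 d | >3 d | ≤5 d | >5 d |
|---|---|---|---|---|---|
| None | 0.1 or 0.2 | 0 | 0 | 0 | 0 |
| Proportional, +0.5 d at the median | 0.1 | −1.3 | −0.8 | −1.1 | −1.0 |
| Fixed, +0.5 d | 0.2 | −4.1 | −2.1 | −2.1 | −1.8 |
| Fixed, +1 d | 0.2 | −8.3 | −4.0 | −4.0 | −3.8 |
| Fixed, −1 d | 0.2 | +7.6 | +4.0 | +4.9 | +3.5 |
| Proportional, −1 d at the median | 0.2 | +5.6 | +4.0 | +4.1 | +5.3 |

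(Zero means within 0.15.)

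**Effect of the cut.** If the short group is strictly under 3 days, as item 3 literally reads, the fixed +1 and −1 day cases at slope 0.2 become about −14 and +10.

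**Stay-glucose link differing by arm, no shift in stay** (lower-slope arm minus higher-slope arm):
- Slopes 0.18 and 0.22: about +3 (≤3 days) and −3 (>5 days).
- Slopes 0.1 and 0.2: +7.5 and −7.4.
- Slopes 0 and 0.2: about +15 and −15, and about +22 in the strict under-3-day group.

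A separate model (SD 45, median stay 5 days, log-SD 0.6), with correlation 0.3 in one arm and 0 in the other, gives 19.0 in the under-3-day group. In that model, shortening stay by 20% with a common correlation of 0.5 gives at most 6.5, and about 0 when stay is unrelated to glucose.

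**Different days averaged.** Suppose one arm runs 10 mg/dl higher on days 2 and 3 only, equally in every patient. A patient's mean then moves by 10 × min(2, stay − 1)/(stay − 1):
- stay of 2 or 3 days: 10;
- 4 days: 20/3 = 6.7;
- 6 days: 20/5 = 4.0;
- 10 days: 20/9 = 2.2.

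With no effect on stay, the ≤3-day group reads 10.0 and the >3-day group 4.6 to 4.7, although the effect is the same in every patient.

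**Sampling error.** The 95% half-width is 1.96 × SD × √(2/(81 × share)). At SD 40 to 45, with shares from the assumed stay distribution:
- ≤3 days (31%): 22 to 25 mg/dl;
- >3 days (69%): 15 to 17;
- ≤5 days (66%): 15 to 17;
- >5 days (34%): 21 to 24;
- all patients: 12 to 14.

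**The case against.** The strongest reply is that no bias has been shown. The sample size assumes equal glucose in the two arms, both arms share one titration scheme, and no passage says that either formulation changes stay. All of that stands. A reader might infer that item 3 will give a biased answer, but the documents do not support this. They plan to test for an effect on stay, and open-label care makes one possible, no more. What remains is that the comparison lacks the protection of randomisation and is not labelled accordingly.

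A reader might instead infer that any bias must be too small to matter, being below the 18 mg/dl margin. That is not supported either. The result depends on which scenarios are run and where the groups are cut, and an arm-dependent link can exceed 18.

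A reader might also infer that item 3 is singled out by having no analysis method. It is not. The endpoint list in Section IV.g is introduced with the word include and also omits items 1, 2, 4, 5 and 9. Item 3 uses the primary variable, whose methods are given. Those methods would, however, still be applied within groups defined by stay. The adjustment for stay in Section IV.g concerns event counts and does not help here.

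Finally, the cut points could be read as three bands (under 3, 3 to 5, over 5 days), which would place stays of exactly 3 and 5 days. This is an ambiguity of wording, not an analysis error.

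**Conclusion.** The point holds as a minor one. Item 3 is presented as a treatment-group comparison but conditions on an outcome of treatment. Bias needs two things together: a relation between stay and glucose, and a treatment effect on stay or on that relation. Glucose influencing discharge in the same way in both arms is not enough. If treatment changes stay only through glucose, a true 9 mg/dl difference still reads 7.8 to 8.9.

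No size can be derived from the documents. Under the assumptions above it ranges from 0, through about 1 to 14 mg/dl for a shift of 0.5 to 1 day, to beyond the margin for a strongly arm-dependent link. The mixing of hospital days arises even when stay is unaffected. The split does not alter the all-patient primary comparison or the sample size, and within-group sampling error exceeds most of these figures.

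**What to change.** Label item 3 descriptive and state that it is not a randomised treatment comparison. State which group stays of exactly 3 and 5 days belong to. Analyse length of stay only as an outcome, under item 8. This costs a few lines of SAP text.

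For the early-versus-late question, an option is to add a treatment-by-day term to the repeated-measures or mixed model already planned in Section IV.g. It would have one prespecified early window, for example days 2–3, in all randomised patients with glucose after day 1. The inpatient flow chart already schedules glucose on days 1 to 10, so no new data are needed.

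This option has two costs. It answers a question about hospital days, not about patients with short or long stays. It also assumes that values after discharge are missing at random: in the assumed model 12% of patients have no day-3 value and 66% no day-6 value. With a fixed 1-day earlier discharge in one arm, slope 0.2 and no true effect, the days 2–3 contrast is itself off by 2.9 mg/dl, against 7.6 in the ≤3-day group.

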We plan to study a total of 180 randomized patients with a known history of T2D, age > 18 years, treated with diet alone, any combination of oral antidiabetic agents, GLP1-RA (except long-acting agents: albiglutide, albiglutide and weekly exenatide) or insulin therapy (except degludec or glargine U300). Patients included within this study will be determined by the set of inclusion and exclusion criteria.

VI.b. Inclusion Criteria:

1. Males or females between > 18 years admitted to a general medicine or surgical service.
2. Known histories of T2D treated with either diet alone, oral monotherapy, any combination of oral antidiabetic agents, short-acting GLP1-RA (exenatide, liraglutide) or insulin therapy with the exception of degludec and glargine U300.
3. Subjects must have a randomization BG > 140 mg and < 400 mg/dL without laboratory evidence of diabetic ketoacidosis (bicarbonate < 18 mEq/L, pH < 7.30, or positive serum or urinary ketones).

VI.c. Exclusion Criteria:

1. Subjects with increased BG concentration, but without a known history of diabetes.
2. Admission or pre-randomization BG ≥ 400 mg/dl
3. Patients treated with degludec or glargine U300, or with long-acting weekly GLP1-RA (weekly exenatide, dulaglutide or albiglutide).
4. Patients with acute critical or surgical illness admitted to the ICU or expected to require admission to the ICU.
5. Patients with clinically relevant hepatic disease (diagnosed liver cirrhosis and portal hypertension), corticosteroid therapy, or impaired renal function (eGFR < 30 ml/min).
6. Mental condition rendering the subject unable to understand the nature, scope, and possible consequences of the study.
7. Female subjects who are pregnant or breast-feeding at time of enrollment into the study.

VI.d. Withdrawal Criteria

1. The subject may withdraw at will at any time.
2. The subject may be withdrawn from the trial at the discretion of the investigator due to a safety concern or if judged non-compliant with trial procedures or included in contravention to the inclusion and/or exclusion criteria.
3. Subject admitted to the ICU who required continuous intravenous insulin infusion to maintain glycemic control.
4. Pregnancy or intention to become pregnant.
5. Treatment with oral or injectable corticosteroid (equivalent or higher than prednisone 5mg/day), parenteral nutrition and immunosuppressive treatment after randomization.

Treatment Failure Criteria

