Subjects with persistent hyperglycemia (≥ 2 glucose readings ≥ 400 mg/dL, ≥ 3 consecutive glucose readings > 280 mg/dL, or with a mean daily blood glucose concentration ≥ 280 mg/dL) and no treatable intercurrent cause for the hyperglycemia has been identified, will be considered as treatment failure and discontinued from the study. If needed, subjects will be started on continuous insulin infusion.

VII. Study Sites: This study will be performed at Grady Memorial Hospital, Emory University Hospitals, Atlanta, GA, Minneapolis Medical Research Foundation-Hennepin Medical Center, Minneapolis, and The Cleveland Clinic Foundation, Ohio.

VIII. CLINICAL MANAGEMENT GUIDELINES

VIII.a. Admission Laboratory Studies

Standard of care laboratory studies including glucose, HbA1C, and chemistry will be measured on admission and as determined by the treating physician.

For **research purposes** a blood sample will be obtained to measure HbA1C at 1 month and 3 months after discharge. In addition, a urine pregnancy test will be performed, when clinically indicated prior to randomization (in female subjects of child bearing potential only).

VIII.b. Assessment and Monitoring of Hospital Mortality

The investigators and research team will follow study subjects daily and the presumed cause of death will be recorded. Information on the attending physician’s summary of events surrounding subject’s demise will also be documented.

VIII.c. Assessment and Monitoring of Nosocomial Infections

Nosocomial infections will be diagnosed based on standardized CDC criteria (40). New nosocomial infections will not be diagnosed until 48 hours after study initiation to minimize the chance that the infection was actually present (but undiagnosed) prior to study initiation.

The investigators will review each subject’s records regarding potential new infection diagnosis daily on each weekday from Monday to Friday. Data from the weekends will be collected on the following Monday. The coded infection diagnosis and the presumed causative microorganism will be determined daily on a Monday to Friday basis, with weekend data entered on the following Monday.

Aim 1. Inpatient Arm – Flow Chart

Visit Type	Hosp- Day 1	Hosp- Day 2	Hosp- Day 3	Hosp- Day 4	Hosp- Day 5	Hosp- Day 6	Hosp- Day 7	Hosp- Day 8	Hosp- Day 9	Hosp- Day 10
Visit #	1	2	3	4	5	6	7	8	9	10
Time-days	1	2	3	4	5	6	7	8	9	10
Inf. consent	x									
Inclusion/excl criteria	x									
Randomization	x									

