Withdrawal criteria	x	x	x	x	x	x	x	x	x	x
Dose adjustment		x	x	x	x	x	x	x	x	x
Efficacy										
Vital signs ¹	x									x
Phys Exam ¹	x									x
Body weight	x									x
BMI	x									x
HbA1c	x									
Fasting BG	x	x	x	x	x	x	x	x	x	x
Pre-meal BG	x	x	x	x	x	x	x	x	x	x
Safety										

Adv events	x	x	x	x	x	x	x	x	x	x
Hypoglycemia	x	x	x	x	x	x	x	x	x	x
Urine pregnancy test	x									x
Trial material										
Drug dispense ²	x									

¹At time of study enrollment and hospital discharge ²As needed

Flow Chart: Aim 2, Outpatient Study

Visit Type	Hospital Day 1	TC	Clinic visit	TC	TC	TC	Clinic visit
Visit #	1	2	3	4	5	6	7
Time-wks	0	2	4	6	8	10	12
Inf. consent	x						
Incl/excl criteria	x						
Randomization	x						
Withdrawal criteria		x	x	x	x	x	x
Drug Compliance		x	x	x	x	x	x
Dose adjustment		x	x	x	x	x	x
Efficacy							
Vital signs	x		x				x
Phys Exam	x		x				x
Body wgt	x		x				x
BMI	x		x				x
HbA1c	x		x				x
Fasting BG	x		x				x
Safety							
Adv events	x	x	x	x	x	x	x
Hypoglycemia	x	x	x	x	x	x	x
Urine pregnancy test	x		x				
CMP or BMP	x		x				x
Trial material							
Drug dispense	x		x				
Drug account	x		x				x

IX. Potential Risks to the Subject:

IX.a. Hypoglycemia. It is possible that following the proposed protocol, patients receiving insulin glargine U300 and U100 may develop hypoglycemia. The risk of hypoglycemia in non-ICU patients treated with subcutaneous insulin is between 5–30% (12, 17, 41, 42). The number of hypoglycemia will be analyzed statistically. For the purpose of this analysis, hypoglycemia is defined as a BG < 70 mg/dL. Severe hypoglycemia is defined as BG < 40 mg/dL.

X. Protection against risks:

We will follow safeguards to minimize the risk to our subjects: a) we will carefully monitor capillary BG at the bedside using a hand-held glucose meter, b) only experienced nurses/or phlebotomist will draw blood samples, and c) women of reproductive age who are sexually active will undergo a urine pregnancy tests prior to participation in the study. To prevent significant clinical events, no patients with history of significant liver, renal impairment or cardiac failure will be recruited in this study.

X.a. Hypoglycemia: We expect that approximately 10% in the inpatient setting and ~20% in the outpatient (post-discharge) arm will experience one or more episodes of hypoglycemia. To minimize the risk of hypoglycemia, the starting dose will be reduced in the basal bolus insulin regimen (TDD: 0.3 units

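### Hypoglycemia event rates use length of hospital stay as exposure, while the schedule shows hypoglycemia collection for days 1-10 only and patients can leave the study in hospital; exposure should be days under observation.

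*Combined protocol and SAP*

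**What the plan says.** Section IV.c, items 6 and 7, defines two measures each for hypoglycemia (BG below 70 mg/dl) and severe hypoglycemia (BG below 40 mg/dl): the number of patients affected, and the "number of events adjusted by length of stay (event rate"). Item 8 makes length of stay a secondary outcome in its own right. Section IV.g (Data Analysis), under the secondary endpoints, analyzes event counts by "Poisson regression (or Negative Binomial regression) that adjusts for the length of hospital stay to assess the difference in the count outcome". It does not say whether the adjustment is an offset or a covariate.

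Three other places bear on when events are recorded:

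- The Aim 1 flow chart marks the hypoglycemia and adverse-event rows for hospital days 1 to 10 and has no later column.
- The primary glucose average in IV.c uses values "collected after the first day of therapy during the hospital stay (up to 10 days"). That limit is written for the primary outcome, not for items 6 and 7.
- Under the Treatment Failure Criteria, patients with persistent hyperglycemia "will be considered as treatment failure and discontinued from the study". Under VI.d, "The subject may be withdrawn from the trial at the discretion of the investigator", among other withdrawal grounds.

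Nowhere is exposure defined as days under observation, and nowhere does the plan say whether hypoglycemia is still recorded after day 10 or after a patient leaves the study.

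**The concern.** A rate needs a denominator covering the same days as its numerator. Length of stay has no upper limit and runs to discharge. It may also begin before the first study dose. If event collection ends at day 10 or at discontinuation, the later hospital days add exposure but cannot add events.

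Fewer hypoglycemic events with U300 is a stated hypothesis of Aim 1. Discontinuation could also be related to treatment: failure is defined by persistent hyperglycemia, the trial is open label, and the introduction notes that U300 reaches steady state only after the second or third day. An arm that loses more patients to hyperglycemia would carry more unobserved days in its denominator and would appear to have less hypoglycemia. The documents do not indicate which arm that would be, or whether the arms will differ.

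**Working it through.** **Inputs from the documents.** There are 90 patients per group, and X.a gives the expected inpatient hypoglycemia: "We expect that approximately 10% in the inpatient setting". The plan states no event rate, stay distribution or discontinuation rate by arm, so there is no figure of its own to reproduce on this point. The sample-size calculation concerns mean glucose and does not enter.

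**Assumptions.** The event rate is constant while on study. Collection stops at day 10 or at discontinuation. Stays are alike in both arms. The stay distributions and discontinuation shares below are assumed.

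**Formula.** With a constant rate, the stay-based rate equals the true rate times F = (sum of observed days) / (sum of days of stay). The apparent rate ratio when the true ratio is 1 is F in one arm divided by F in the other.

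**Step 1, one patient followed to day 10.** F = 10/stay: 10/12 = 0.83, 10/14 = 0.71, 10/20 = 0.50. For a stay of 10 days or less without discontinuation, F = 1.

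**Step 2, geometric stays with mean m.** Expected days observed up to day k are m × (1 − (1 − 1/m)^k).

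- m = 5, day-10 limit only: 5 × (1 − 0.8^10) = 4.463 days, so F = 0.89. Discontinuation on day 1, 2 or 3 with equal chance gives (1 + 1.8 + 2.44)/3 = 1.747 days. With 10% discontinued: 0.9 × 4.463 + 0.1 × 1.747 = 4.191. With 2%: 0.98 × 4.463 + 0.02 × 1.747 = 4.409. Apparent ratio: 4.191/4.409 = 0.951.
- m = 7: the day-10 limit gives 5.502 days (F = 0.79), and discontinued patients average 1.816 days. With 10%: 5.133. With 2%: 5.428. Apparent ratio: 0.946.

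**Step 3, gamma stays (coefficient of variation 0.8, rounded up to whole days), discontinuation at day 3.**

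| Gamma mean (after rounding up) | F, day-10 limit only | F, 10% discontinued | Ratio, 15% vs 5% | Ratio, 20% vs 0% |
|---|---|---|---|---|
| 4 (4.5) | 0.96 | 0.92 | 0.96 | 0.92 |
| 5 (5.5) | 0.92 | 0.88 | 0.95 | 0.91 |
| 7 (7.5) | 0.82 | 0.78 | 0.94 | 0.89 |
| 10 (10.5) | 0.69 | 0.65 | 0.94 | 0.88 |

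With 10% discontinued, each arm's rate is therefore 8% to 35% too low. The day-10 limit acts on both arms and largely cancels in the ratio. Unequal discontinuation moves the ratio.

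**Step 4, effect on the test.** An expected 10% of patients over an assumed 5 days gives −ln(0.9)/5 = 0.021 events per day. The two-sided type I error (nominal 5%) was simulated with 20,000 trials, 90 per arm, gamma mean 7, and 15% versus 5% discontinued:

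| Events per day | Length of stay | Observed days |
|---|---|---|
| 0.021 | 4.8% | 4.2% |
| 0.05 | 6.0% | 4.5% |
| 0.10 | 7.5% | 4.8% |

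Using observed days keeps the error below 5% throughout. At the protocol's expected level, the stay-based test is not inflated either.

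**The case against.** The strongest reply is that the plan never says recording ends at day 10 or at discontinuation. The day-10 end is read from the last column of the flow chart, and a footnote on the vital-signs and examination rows treats that column as discharge. Leaving the study is not the same as ending data collection. If events are recorded to discharge for everyone, numerator and denominator agree, apart from any days before randomization. This stands, and it is why the point is conditional.

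The size can also be challenged. Item 3 of IV.c splits stays at 3 and 5 days, which suggests many short stays with no mismatch after randomization. Ten percent of 90 is 9 patients per arm. At one event each, the standard error of the log ratio is √(1/9 + 1/9) = 0.47, whereas a ratio of 0.95 is a shift of only 0.05. Randomization balances days before allocation in expectation, so they lower both rates without favoring an arm. All of this stands.

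Two further inferences are not supported. One is that a longer stay in itself favors an arm: it does so only where it adds unobserved days. The other is that the plan enters length of stay as a covariate and so conditions on a post-randomization outcome. The count model's wording is open, and the label event rate in IV.c points to a denominator. Days under observation are also determined after randomization.

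What the reply does not remove is the exposure rule itself. As written, it counts the whole hospital stay whether or not events could be recorded on those days.

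**Conclusion.** The concern holds in conditional form. The stated denominator is the hospital stay, the schedule shows hypoglycemia for days 1-10 only, patients can leave the study while in hospital, and no rule aligns the two. If collection stops at day 10 or discontinuation, the rate is understated for the patients concerned, and the rate ratio leans toward the arm with more or earlier discontinuation. With similar stays and the assumed discontinuation shares of 10% versus 2% or 15% versus 5%, a true ratio of 1 becomes about 0.94-0.96. It takes 20% versus 0% to reach 0.88-0.92.

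A reader might infer that the rates are certain to be biased, or that the hypoglycemia hypothesis as a whole is compromised. The documents support neither. The first depends on an unstated collection rule. As to the second, the number of patients with hypoglycemia, tested by chi-square, Fisher or Cochran-Mantel-Haenszel methods, has no stay denominator and is untouched. The point is still worth correcting, because the stated rule can count days without event capture and the remedy costs almost nothing.

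**What to change.** In IV.c items 6 and 7, and under the secondary endpoints in IV.g (Data Analysis), replace length of stay with days under observation for hypoglycemia. These run from first study dose to the earliest of discharge, day 10 or end of data collection. Count only events inside that window, and enter the logarithm of those days as an offset in the Poisson or negative binomial model.

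Alternatively, state that events are collected to discharge for all randomized patients, including those discontinued or withdrawn from treatment, with exposure still starting at first study dose.

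The offset makes numerator and denominator match. It does not show what the rate would have been after a patient left observation, so discontinuations and observed days should be reported by arm.

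The cost is a change of wording, plus confirming that the date on which collection ended is recorded for each patient. The documents do not show that it is.
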